9.2.5 Sample Size/Power Considerations

Sample size for this study was determined based on the results from the phase 2a study. In the phase 2a study, efficacy was demonstrated in 34 subjects treated with ENT-01, with a mean change from baseline in CSBMs of 2.4. In that study, of the 72 randomized subjects, 64 (89%) were evaluable for the primary efficacy endpoint analysis. Randomization was 3:1 to active treatment or placebo; 64

subjects were randomized to active treatment and 18 subjects were randomized to placebo. The study assumed an increase from baseline in weekly CSBM rate in the Fixed Dose period of 2.4 and 0.5 for the active drug and placebo-treated subjects, respectively, and an SD of 2.0. amended.

In this protocol amendment, enrolling an additional 80 subjects in a 1:1 randomization will yield a conditional power of approximately 93% and an additional 60 subjects will yield a conditional power of 88%. This is based on the additional subjects having a least squares mean change from baseline for the Fixed Dose Period of 3.55 and 1.28 for ENT-01 and placebo, respectively, and a common standard deviation of 3.88. The power calculations incorporated a 10% drop-out rate. These parameter estimates and conditional power calculations are based on the results of the initial cohort of subjects in the Phase 2b study.

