1.2.3 Exploratory Objectives

The exploratory objectives include:

- To determine the decrease in efficacy in the blinded placebo withdrawal and washout periods.
- To collect information on the effect of ENT-01 on motor and non-motor symptoms of Parkinson's disease including mood, memory, sleep, and hallucinations/delusions.
- To collect information on the effect of ENT-01 on levodopa absorption.
- To collect information on the effect of ENT-01 on the stool microbiome.

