2. STUDY DESIGN

2.1. Synopsis of Study Design

This study will be conducted as a multicenter, randomized, double-blind, placebo-controlled study in patients with Parkinson's Disease and constipation.

This study has two parts. The first part of this randomized approximately 72 subjects in a 3:1 to treatment or placebo ratio (double-blind), with approximately 54 subjects allocated to the treatment groups and approximately 18 to placebo. In the second part of the study, an additional 80 patients (approximately) will be randomized 1:1 to treatment or placebo (double-blind) with approximately 40 subjects allocated to each group.

In both parts of the study, the study was conducted as a multicenter, randomized, double-blind, placebo-controlled study. A subject's total study duration was no more than 10 weeks and total active dosing days was a maximum of 25 days.

During the active dosing period, patients will be able to increase/adjust their dose every three days. This is called the Dose Adjustment period. After the subject documents two complete spontaneous bowel movements in three days, the subject will fix at the dose for the remainder of the study. This is called the Fixed Dose period. After completing up to 25 days of dosing, all subjects will be given placebo for 2 weeks (single-blind) followed by 4 weeks of wash-out.

Figure 1. Visit Schedule Overview					
Visit 1	Visit 2	Visit 3	Visit 4	Visit 5	Visit 6
Screening	Randomization and Drug Dispensation	Follow up	Single Blind Placebo Withdrawal	Wash Out	End of Study
Day -14	Day 1	Day 11 +/- 1 day	Day 25 - 3 days	Day 39 +/- 2 days	Day 69 +/- 3 days

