4.6.3 Analysis of the Primary Efficacy Endpoint

The primary efficacy endpoint is the change from baseline in weekly CSBM rate during the Fixed Dose period. The primary analysis will be based on the Fixed Dose Population. The primary efficacy analysis will be performed via an analysis of covariance (ANCOVA) model with change from baseline in weekly CSBM rate as the dependent variable, treatment (ENT-01 or placebo) as the independent variable, and baseline weekly CSBM rate as a covariate.

As a supplemental analysis, the treatment effect for the primary efficacy endpoint will be summarized by the weekly CSBM rate subgroups (0 – 0.9, 1.0 – 3.0). The analysis will be performed for both Efficacy Evaluable population and Fixed Dose population.

The study will be considered a success if the p-value for the comparison of treatment groups from the ANCOVA model using the Fixed Dose population is significant (p<0.05).

Change from baseline in weekly CSBM rate will also be summarized by the specific fixed dose for patients. These summaries will be descriptive in nature only and no inferential statistics will be performed.

A linear trend test for weekly CSBM rate within each treatment group across baseline, fixed dose, and single blind periods will be conducted by using mixed model repeated measures (MMRM) methods, where the Baseline, Fixed Dose, and Single Blind periods are assigned values of 0,1, and 2 respectively for modeling purposes. Baseline CSBM rate (0-0.9/1.0-3.0) is included as a factor, with subject intercept and slope as random effects in the mixed model. The trend test will also be conducted across all subjects, including both Placebo and ENT-01 treatment groups in the model as a factor (fixed effect).

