4.6.4 Analysis of Secondary Efficacy Endpoints

All secondary efficacy endpoints will be analyzed based on both the Efficacy Evaluable population and Fixed Dose population.

Continuous Secondary Efficacy Endpoints

The following are the set of continuous secondary efficacy endpoints:

- Change from baseline in the weekly SBM rate during the Fixed Dose period
- Change from baseline in stool ease of passage during the Fixed Dose period
- Change from baseline in stool consistency during the Fixed Dose period
- Change from baseline in suppository/enema use during the Fixed Dose period
- Change from baseline in the overall scores and individual items of PAC-SYM and PAC-QOL subjective assessments during the Fixed Dose period

All continuous secondary efficacy endpoints will be analyzed in the same manner as the primary efficacy endpoint with treatment, baseline CSBM strata, and corresponding baselines as the independent variables in the ANCOVA model and also by summarizing change from baseline

by the specific fixed doses. The same linear trend tests will also be performed on these endpoints.

Categorical Secondary Efficacy Endpoints

The following are the set of categorical secondary efficacy endpoints:

- Dichotomous prokinetic bowel response during the Fixed Dose period
- Dichotomous SBM bowel response during the Fixed Dose period
- Frequency of dose adjustments in the Dose Adjustment period from the initial starting dose to the subject's fixed dose

The dichotomous endpoints will be summarized using count data, frequencies, and odds ratios for comparisons between groups, and analyzed using Fisher's exact test. If there are sufficient numbers in each strata, the analysis may also be performed using the Cochran-Mantel-Haenszel (CMH) test adjusting for the baseline CSBM strata, to compare ENT-01 versus placebo. The frequency of dose adjustment will be summarized by treatment groups and baseline CSBM strata and no formal test will be performed to compare the treatment groups.

Summary statistics will also be presented by specific fixed dose groups for descriptive purposes only.

Time to Event Secondary Efficacy Endpoints

The following are the set of time to event secondary efficacy endpoints:

- Time to first CSBM in the Fixed Dose period
- Time to first SBM in the Fixed Dose period
- Time to first rescue medication use in the Fixed Dose period

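### The supplementary 0/1/2 linear trend test gives the Fixed Dose period no weight on complete data, so it measures off-drug persistence and not a trend that includes the on-drug response (minor)

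*SAP*

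**What the plan says.** SAP 4.6.3 defines the primary ANCOVA and the success criterion first. It then adds "A linear trend test for weekly CSBM rate within each treatment group across baseline, fixed dose, and single blind periods", fitted by mixed-model methods, "where the Baseline, Fixed Dose, and Single Blind periods are assigned values of 0,1, and 2 respectively for modeling purposes". The baseline CSBM stratum is a factor, "with subject intercept and slope as random effects in the mixed model". No other residual structure is stated.

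A pooled version follows: "The trend test will also be conducted across all subjects, including both Placebo and ENT-01 treatment groups", with treatment as a fixed factor. No treatment-by-period term is given.

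SAP 4.6.4 extends the test to the continuous secondary endpoints: "The same linear trend tests will also be performed on these endpoints". SAP 4.2 sets formal efficacy tests at two-sided 0.05.

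The period scored 2 is off drug for everyone: "all subjects will be given placebo for 2 weeks (single-blind) followed by 4 weeks of wash-out" (SAP 2.1). One exploratory objective for that phase is "To determine the decrease in efficacy in the blinded placebo withdrawal and washout periods" (SAP 1.2.3).

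**The concern.** The scores assume that the outcome moves in equal steps in one direction from baseline, through treatment, to placebo withdrawal. The design points to another shape: a rise on drug, then some loss once all subjects take placebo. A straight line cannot show a rise followed by a fall.

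The test is described as a trend across all three periods and sits under the primary endpoint. A reader of the report would naturally take it as evidence about response to treatment. A null result could be read as lack of effect when the drug worked and wore off. A significant result could be read as on-drug response when it reflects carry-over or, within one arm, drift unrelated to drug. The same risk recurs for each continuous secondary endpoint.

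**Working it through.** The documents give no expected slope, power or sample size for this test, so there is no stated figure to reproduce. The check derives what the slope estimates.

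**Inputs**
- Scores: t = 0 (Baseline, BL), 1 (Fixed Dose, FD), 2 (Single Blind, SB), from SAP 4.6.3.
- Covariance: random subject intercept and slope, from SAP 4.6.3.
- Assumed Fixed Dose changes: "least squares mean change from baseline for the Fixed Dose Period of 3.55 and 1.28 for ENT-01 and placebo" (Protocol 9.2.5).
- Assumption, not in the documents: the share r of the Fixed Dose gain that persists into the Single Blind period, taken from 0 to 100%.

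**Step 1: least-squares slope.** The mean score is 1, so

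slope = [(0−1)·BL + (1−1)·FD + (2−1)·SB] / [(−1)² + 0² + 1²] = (SB − BL)/2.

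The weights on (BL, FD, SB) are (−0.5, 0, +0.5).

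**Step 2: the mixed model.** Write X = [1, t] and V = XGX′ + σ²I for one subject. Then VX = X(GX′X + σ²I), so V maps the column space of X into itself. Generalised and ordinary least squares therefore coincide on complete data, whatever G and σ² are. The stratum factor is constant within subject and leaves the slope unchanged. Direct computation under three assumed sets of variance components gave (−0.5, 0, +0.5) each time. In 40 simulated complete data sets of 40 subjects with full wear-off, the REML slope agreed with (SB − BL)/2 to four decimals.

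**Step 3: size.** If a share r of a gain D persists, SB − BL = r·D and the slope is r·D/2. The baseline value cancels.

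| Share retained (assumed) | ENT-01, D = 3.55 | Placebo, D = 1.28 |
|---|---|---|
| 0% | 0.00 | 0.00 |
| 25% | 0.44 | 0.16 |
| 50% | 0.89 | 0.32 |
| 75% | 1.33 | 0.48 |
| 100% | 1.78 | 0.64 |

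With full wear-off both arms have slope 0, although the assumed on-drug difference between arms is 3.55 − 1.28 = 2.27.

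**Step 4: departures from the complete-data result**, for the ENT-01 gain with full wear-off. The slope weights sum to zero, so here the slope equals the Fixed Dose weight times 3.55.
- Missing Single Blind data, with assumed variance components: 5% missing gives a slope of about 0.05 to 0.11, 10% gives 0.10 to 0.22, and 25% gives 0.29 to 0.58. At 25% the Fixed Dose weight is 0.29/3.55 = 0.08 to 0.58/3.55 = 0.16.
- An unstructured covariance instead, under four assumed sets of values: the Fixed Dose weight runs from −0.12 to +0.05 and the slope from −0.42 to +0.19. The weight can be negative.

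In a Fixed Dose minus Baseline contrast the Fixed Dose mean has weight 1.

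**Step 5: pooled version.** With treatment as a main effect and one common slope, the trend coefficient averages over arms. No term says whether the change over periods differs between ENT-01 and placebo.

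**Step 6: period as a factor.** For the same means with full wear-off, Fixed Dose minus Baseline is +3.55 and +1.28 (between-arm difference 2.27). Single Blind minus Fixed Dose is −3.55 and −1.28 (difference −2.27). Both the rise and the fall are visible.

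**The case against.** The strongest reply is that nothing rests on this test and that the questions it misses are answered elsewhere. Much of that stands.

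- Success depends only on the ANCOVA in the Fixed Dose population (SAP 4.6.3). The trend test does not appear in Protocol 9.2.4. A reader might infer that the 0/1/2 score endangers the trial's conclusion; the documents do not support that.
- A reader might infer that loss of effect on withdrawal goes unanalysed. It does not. SAP 4.6.5 compares arms by ANCOVA on Single Blind change from baseline and again from the Fixed Dose value. This covers CSBM and SBM rates, ease of passage, consistency, suppository and enema use, and the PAC-SYM and PAC-QOL total and subdomain scores.
- A reader might infer that the slope is always zero for an effective drug. That requires complete data and a full average return to baseline over the two placebo weeks, which no passage states. Protocol section 4 plans for 25% early termination, so incomplete data are likely.
- Half of Single Blind minus Baseline is a legitimate persistence measure, and Protocol 4.4 says that the placebo period is there to establish how long the effect lasts.

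What does not stand is the defence of the test as written. Neither document presents the slope as a persistence measure or gives a reason for a linear score. As persistence, it is half of a quantity that SAP 4.6.5 already analyses under a correct name and between arms.

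**Conclusion.** The point holds as a minor one, confined to a supplementary analysis. On complete data the trend slope is exactly (Single Blind minus Baseline)/2. It carries no information on the Fixed Dose period, the only one of the three in which ENT-01 subjects are analysed on drug. Missing Single Blind data or another residual covariance alters the Fixed Dose weight only modestly: at most about 0.16 in size in the cases examined. For an assumed gain of 3.55 the slope lies between 0 and 1.78, according to how much persists off drug.

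The zero weight is algebra. The retention shares, missing-data shares and variance components are assumptions, because the documents give none of them. The pooled version does not compare arms. The primary ANCOVA, the success criterion and the planned withdrawal analyses are untouched. The harm is a supplementary p-value that is easily misread, repeated across the continuous secondary endpoints.

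**What to change.** Either of two changes to SAP 4.6.3 and 4.6.4 is enough.

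1. Replace the 0/1/2 score with period as a three-level factor, and include treatment and treatment-by-period in one mixed model. Report Fixed Dose minus Baseline and Single Blind minus Fixed Dose as between-arm contrasts, labelled supportive, beside the ANCOVAs of 4.6.3 to 4.6.5.
2. Drop the linear trend test and rely on those ANCOVAs.

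The first option costs a short rewording and one changed model statement, and its contrasts overlap with planned ANCOVAs. The second costs only wording. It would leave the individual PAC-SYM and PAC-QOL items without a withdrawal-period test, since SAP 4.6.5 lists only total and subdomain scores. Neither option needs new data.

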4.6.4 Analysis of Secondary Efficacy Endpoints

All secondary efficacy endpoints will be analyzed based on both the Efficacy Evaluable population and Fixed Dose population.

Continuous Secondary Efficacy Endpoints

The following are the set of continuous secondary efficacy endpoints:

- Change from baseline in the weekly SBM rate during the Fixed Dose period
- Change from baseline in stool ease of passage during the Fixed Dose period
- Change from baseline in stool consistency during the Fixed Dose period
- Change from baseline in suppository/enema use during the Fixed Dose period
- Change from baseline in the overall scores and individual items of PAC-SYM and PAC-QOL subjective assessments during the Fixed Dose period

All continuous secondary efficacy endpoints will be analyzed in the same manner as the primary efficacy endpoint with treatment, baseline CSBM strata, and corresponding baselines as the independent variables in the ANCOVA model and also by summarizing change from baseline

by the specific fixed doses. The same linear trend tests will also be performed on these endpoints.

Categorical Secondary Efficacy Endpoints

The following are the set of categorical secondary efficacy endpoints:

- Dichotomous prokinetic bowel response during the Fixed Dose period
- Dichotomous SBM bowel response during the Fixed Dose period
- Frequency of dose adjustments in the Dose Adjustment period from the initial starting dose to the subject's fixed dose

The dichotomous endpoints will be summarized using count data, frequencies, and odds ratios for comparisons between groups, and analyzed using Fisher's exact test. If there are sufficient numbers in each strata, the analysis may also be performed using the Cochran-Mantel-Haenszel (CMH) test adjusting for the baseline CSBM strata, to compare ENT-01 versus placebo. The frequency of dose adjustment will be summarized by treatment groups and baseline CSBM strata and no formal test will be performed to compare the treatment groups.

Summary statistics will also be presented by specific fixed dose groups for descriptive purposes only.

Time to Event Secondary Efficacy Endpoints

The following are the set of time to event secondary efficacy endpoints:

- Time to first CSBM in the Fixed Dose period
- Time to first SBM in the Fixed Dose period
- Time to first rescue medication use in the Fixed Dose period

Time to event endpoints will be summarized using Kaplan-Meier methods and comparisons between treatment groups will be made via log-rank tests, stratified by the baseline CSBM rate. The start date for time to event analyses will be the date of first dose in the fixed dose period.

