9.2.4.2 Secondary Efficacy Endpoint Analyses

Secondary efficacy analyses will be based on the Efficacy Evaluable Population. The comparison of active versus placebo treatment will be tested at the two-sided 0.05 significance level.

The following are the set of continuous secondary efficacy endpoints:

- Change from baseline in the weekly SBM rate during the Fixed Dose period
- Change from baseline in stool ease of passage during the Fixed Dose period
- Change from baseline in stool consistency during the Fixed Dose period
- Change from baseline in suppository/enema use during the Fixed Dose period

All continuous secondary efficacy endpoints will be analyzed in the same manner as the primary efficacy endpoint.

The following are the set of dichotomous secondary efficacy endpoints:

- Pro-kinetic bowel response during the Fixed Dose period
- SBM bowel response to ENT-01 during the Fixed Dose period

For the dichotomous secondary efficacy endpoints, the comparison of the ENT-01 versus placebo treatment groups will be performed by means of Fisher's exact test.

The following are the set of time to event secondary efficacy endpoints:

- Time to first CSBM in the Fixed Dose period
- Time to first SBM in the Fixed Dose period
- Time to first rescue medication use in the Fixed Dose period
- Time to event secondary efficacy endpoints will be summarized using Kaplan-Meier methods, comparisons between treatment groups will be made via log-rank tests.
- For the frequency of dose adjustments in the Dose Adjustment period secondary endpoint, the frequency of the number of dose adjustments a subject has from the initial starting dose to the subject's fixed dose will be summarized by treatment group and baseline CSBM strata.
- For the PAC-SYM and PAC-QOL subjective assessments secondary efficacy endpoints, the overall scores from the Fixed Dose period will be analyzed via an ANCOVA model with treatment as a factor and the subject's corresponding baseline score as a covariate. Additional summaries of the individual items will be performed.

9.2.4.3 Exploratory Efficacy Endpoint Analyses:

The analysis methods for the exploratory efficacy endpoints will be provided in the SAP.

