- Stool-related subjective assessments using the PAC-SYM: Subjective bowel function data is captured using the Patient Assessment of Constipation-Symptoms: The PAC-SYM is a 12-item questionnaire, and each question has a 0 (Absent) – 4 (Very Severe) point response scale. The PAC-SYM overall score is the score obtained by averaging the response from the 12 items. The PAC-SYM scores and change from baseline will be calculated for each scheduled assessment time-point.

- Stool-related subjective assessments using the PAC-QOL: Constipation-related quality of life is assessed using the Patient Assessment of Constipation-Quality of Life. The PAC-QOL is a 28-item questionnaire, and each question has a 5-point ordinal response scale. The PAC-QOL endpoints consist of an overall average score and the four subscale scores (i.e., physical discomfort, psychosocial discomfort, worries/concerns, and satisfaction). The PAC-QOL scores and change from baseline will be calculated for each scheduled assessment time-point.

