4.2. General Statistical Methods and Data Handling

General Methods

All outputs will be incorporated into Microsoft Excel or Word files, sorted and labeled according to the International Conference on Harmonisation (ICH) recommendations, and formatted to the appropriate page size(s).

Tabulations will be produced for appropriate demographic, baseline, efficacy, pharmacokinetic and safety parameters. For categorical variables, summary tabulations of the frequency and percentage within each category (with a category for missing data) of the parameter will be presented. For continuous variables, the mean, median, SD, minimum and maximum values will be presented. Time to event data will be summarized using Kaplan-Meier Methodology using 25th, 50th (median), and 75th percentiles with associated 2-sided 95% confidence intervals, as well as percent of observed event rate and summary statistics for the follow-up time.

Formal statistical hypothesis testing will be performed on the efficacy endpoints with all tests conducted at the 2-sided 0.05 level of significance. Summary statistics will be presented, as well as confidence intervals on selected parameters, as described in the sections below.

For all analyses, baseline will be defined as the most recent measurement prior to the date and time of the administration of ENT-01 or placebo. Therefore, baseline may be on the same day as the dose of study treatment, but prior to the administration of the study treatment.

Computing Environment

All descriptive statistical analyses will be performed using SAS statistical software (Version 9.4), unless otherwise noted. Medical History and Adverse Events will be coding using the latest MedDRA version available upon the study start. Concomitant medications will be coded using the latest World Health Organization (WHO) Drug version available upon the study start.

Methods of Pooling Data

Not applicable to the present study.

Adjustments for Covariates

Statistical analyses for the efficacy endpoints will be adjusted by the randomization strata, the baseline CSBM rate (0 – 0.9 vs. 1.0 – 3.0).

Multiple Comparisons/Multiplicity

Adjustments for multiplicity will not be made for this study.

Subpopulations

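### SAP 4.6.4 turns the protocol's descriptive summaries of 40 PAC-SYM and PAC-QOL items into unadjusted secondary-endpoint tests, while the four PAC-QOL subscales get no planned Fixed Dose comparison

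*SAP*

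**What the plan says.** **Definition of the endpoints.** SAP 2.6.2 and Protocol 3.2 agree. The PAC-SYM endpoint is an overall score, the average of 12 items. For PAC-QOL, "The PAC-QOL endpoints consist of an overall average score and the four subscale scores". Neither document names a single item as an endpoint. Both say that scores and changes from baseline are calculated at each scheduled assessment.

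**Protocol analysis.** Protocol 9.2.4.2 applies ANCOVA to the overall scores from the Fixed Dose period. On the items it says "Additional summaries of the individual items will be performed". It specifies no analysis of the subscales.

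**SAP analysis.** SAP 4.6.4 lists "Change from baseline in the overall scores and individual items of PAC-SYM and PAC-QOL subjective assessments during the Fixed Dose period" as continuous secondary endpoints and continues: "All continuous secondary efficacy endpoints will be analyzed in the same manner as the primary efficacy endpoint". It then adds "The same linear trend tests will also be performed on these endpoints". The section is to be run in both the Efficacy Evaluable and the Fixed Dose populations. SAP 4.2 sets all efficacy tests at two-sided 0.05 and states "Adjustments for multiplicity will not be made for this study".

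**Where the subscales do appear.** SAP 4.6.5 lists the four PAC-QOL subdomain scores, as exploratory endpoints, for the Placebo Withdrawal and Washout periods.

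**Declared changes.** SAP section 5 reports none.

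**The concern.** There are two mismatches. First, the SAP gives 40 single questionnaire items the status of secondary efficacy endpoints and a full set of tests, where the protocol asks only for summaries. An item that reaches 0.05 by chance could then be reported as a significant secondary result. Second, the four subscales, which the definitions do include, are compared between arms only once active drug has stopped. For the period in which treatment is given, no subscale comparison is planned.

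The SAP wording on the items is hard to read as descriptive. Where the same section wants no inference it says so: it excludes formal testing for the frequency of dose adjustment and marks the fixed-dose-group summaries as descriptive. The items carry no such limit.

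At stake is how the secondary results can be read, and whether the SAP matches the protocol as it claims to.

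**Working it through.** The documents give no test count or false-positive rate for these endpoints, so there is no figure of theirs to reproduce first.

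**Inputs**
- PAC-SYM items: 12 (SAP 2.6.2: "The PAC-SYM is a 12-item questionnaire").
- PAC-QOL items: 28 (SAP 2.6.2: "PAC-QOL is a 28-item questionnaire, and each question has a 5-point ordinal response scale").
- Level: 0.05 two-sided per test, unadjusted (SAP 4.2).
- Populations: the two that SAP 4.6.4 names.
- Trend tests per endpoint: three, one in each arm and one across all subjects (SAP 4.6.3).
- Inter-item correlation: not given. Assumed exchangeable at 0.3, 0.5 and 0.7.

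**Number of item tests**
- Items: 12 + 28 = 40, so 40 ANCOVA comparisons per population and 2 × 40 = 80 over both.
- With trend tests: 40 × (1 + 3) × 2 = 320 item-level tests. I do not multiply this figure by 0.05. A trend within one arm is not a treatment comparison, and it can be real even if ENT-01 does nothing, for example through a placebo response.
- Fixed Dose comparisons of the four PAC-QOL subscales: 0.

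**Expected false positives, if ENT-01 affects none of the 40 items**
- Either direction: 40 × 0.05 = 2.0 per population.
- In favour of ENT-01: 40 × 0.025 = 1.0 per population.
- Over two populations: 80 × 0.05 = 4.0. The populations overlap heavily, so these are largely the same findings seen twice.

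These counts do not depend on the correlation.

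**Chance of at least one false positive among the 40, one population**
- Independent items, either direction: 1 − 0.95^40 = 0.871.
- Independent items, in favour of ENT-01: 1 − 0.975^40 = 0.637.
- Correlated items: 40 equicorrelated normal statistics, with rejection at |Z| > 1.96, or at Z > 1.96 for the favourable direction.

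| Assumed correlation | Either direction | In favour of ENT-01 |
|---|---|---|
| 0 | 87% | 64% |
| 0.3 | 75% | 40% |
| 0.5 | 57% | 29% |
| 0.7 | 38% | 19% |

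**The same calculation for the declared scores.** Two overall scores plus four subscales make 6 tests per population. Expected false positives: 6 × 0.05 = 0.30. Chance of at least one if independent: 1 − 0.95^6 = 0.265.

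**The texts side by side**

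| | Endpoint definition (Protocol 3.2, SAP 2.6.2) | Protocol 9.2.4.2 | SAP 4.6.4, Fixed Dose |
|---|---|---|---|
| Overall scores | named | ANCOVA | ANCOVA and trend tests |
| Four PAC-QOL subscales | named | no analysis stated | not listed |
| 40 individual items | not named | summaries | ANCOVA and trend tests |

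On the items, the SAP departs from the protocol. On the subscales, both analysis sections fall short of the shared definition.

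**The case against.** The strongest reply is that no decision rests on these tests. SAP 4.6.3 makes study success depend only on the primary ANCOVA in the Fixed Dose population. This is a phase 2b trial whose secondary aim here is to collect information, and SAP 4.2 openly states that multiplicity is not controlled, so readers are warned. That stands, and it limits the harm to the secondary results. It does not explain why the items are labelled secondary endpoints, or why section 5 reports no change.

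A reader might infer that the subscale results during treatment will not exist, or that the PAC-QOL endpoint goes untested. The documents support neither. SAP 2.6.2 has PAC-QOL scores and changes calculated at each scheduled assessment, and the schedule of events includes PAC-QOL at Visits 3 and 4. SAP 4.6.5 also repeats the later-period changes from an end-of-Fixed-Dose baseline, which needs those values. The overall PAC-QOL score is tested. What is missing is a planned between-arm comparison of one component of the endpoint.

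Nor is the subscale gap peculiar to the SAP, since Protocol 9.2.4.2 has it too. Adding subscale tests therefore goes beyond the protocol's analysis section and should be declared.

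The 87% is also open to challenge. It needs independence between items of the same questionnaires, which is implausible, and it counts both directions. It belongs at the upper end of the range.

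**Conclusion.** The point holds in this form. SAP 4.6.4 makes formal, unadjusted secondary tests of 40 items that the protocol only summarises, and does not declare the change. The four PAC-QOL subscales, part of the defined endpoint, have no Fixed Dose treatment comparison in either analysis section.

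The size is 2.0 expected false-positive items per population, 1.0 of them favouring ENT-01. This rests on a null effect for all 40 items but not on any correlation. The chance of at least one in either direction runs from 87% under independence down to about 38% at an assumed correlation of 0.7.

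It would be wrong to read this as inflation of the trial's primary type I error: the primary test and the success criterion are untouched. The change should be made, but the consequence is confined to the interpretation of secondary results.

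**What to change.** 1. In SAP 4.6.4, replace the PAC entry with the PAC-SYM overall score, the PAC-QOL overall score and the four PAC-QOL subscale scores, each as change from baseline in the Fixed Dose period, analysed by ANCOVA.
2. State that the 12 PAC-SYM and 28 PAC-QOL items are presented by descriptive statistics only, without p-values and without trend tests. This restores the protocol's rule.
3. In SAP section 5, record the subscale ANCOVA as an addition to Protocol 9.2.4.2.

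The cost is SAP wording and fewer inferential tables. Data collection, visits and sample size do not change, and the subscale scores are already to be calculated. The price in multiplicity is four more tests per population in place of 40.
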